11.2 Analysis Datasets or Populations

Full Analysis Set

Each DB treatment period will have a full analysis set (FAS), which will include all randomized patients who during the treatment period took at least one dose of study medication, have at least one post-baseline efficacy time point assessment during the 2 hours postdose, and did not use a second dose of study medication or rescue medication prior to the data collection of the 2 hours postdose time point (inclusive).

Safety Population

The safety population will include all patients who receive at least one dose of DB study medication during both treatment periods.

Additional information is included in the SAP. The SAP will serve as a compliment to the protocol and supersedes it in case of differences.

Per Protocol Population

The per protocol (PP) population will include all DB1 FAS patients who have at least 1 post-baseline primary endpoint assessment, who have no significant protocol deviations that will impact the collection or interpretation of the primary endpoint data during the DB1 treatment period. Identification of all patients in the PP population will be determined before the database lock and unblinding.

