8. EFFICACY

8.1. PRIMARY EFFICACY ENDPOINT AND ANALYSIS

8.1.1. Primary Analysis of the Primary Endpoint

The primary efficacy endpoint is the proportion of subjects who are free from headache pain at 2 hours after the first dose of study medication taken for a migraine attack with moderate to severe headache pain during the DB1 treatment period (ie, headache pain rating of moderate [Grade 2] or severe [Grade 3] predose reduced to none [Grade 0] at 2 hours postdose). The primary efficacy endpoint will be analyzed using Fisher's exact test.

Proportions of subjects free from headache pain at 2 hours postdose will be calculated as the number of subjects who are pain-free at 2 hours postdose divided by the number of subjects with non-missing assessment at 2 hours postdose. Missing primary efficacy endpoint data will be imputed using the last observation carried forward (LOCF). Results based on the LOCF data and the observed data will be displayed separately.

The number of subjects with response, the number of subjects with non-missing assessment, proportions for the DFN-02 10 mg and placebo groups, 95% exact CIs for those proportions, the odds ratio for response, and the corresponding p-value will be presented for the comparison between two treatment groups for the FAS1. This analysis will exclude subjects who took a second dose of study medication or rescue medication prior to the data collection of the 2 hours postdose time point (inclusive). The analysis will also be performed using the PPS.

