8.2. SECONDARY EFFICACY ENDPOINTS AND ANALYSES

The secondary efficacy endpoints that involve proportions of subjects who have a response will be summarized by treatment group and will be analyzed using the LOCF for missing secondary efficacy endpoint data.

Secondary efficacy endpoint analyses will be conducted as indicated for the FAS1 and FAS2 and will exclude subjects who took a second dose of study medication or rescue medication prior to the data collection of the 2 hours postdose time point (inclusive).

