9.1. EXTENT OF EXPOSURE AND COMPLIANCE WITH STUDY MEDICATION

In this trial, subjects are considered compliant if they treat a migraine attack with study medication. Study medication exposure will be summarized by treatment group and overall for the SS, FAS1, and FAS2. By definition of the FAS1 and FAS2, each subject in those cohorts is considered compliant.

Subjects are expected to administer one dose of study medication within 1 hour of experiencing moderate or severe migraine pain. If after 2 hours a subject does not experience sufficient relief, the subject may take a second dose of study medication for the same migraine attack. Two nasal sprays will be dispensed to each subject for each DB treatment period.

The following will be presented for the SS, FAS1, and FAS2:

- The total number of study medication doses
- The number of days since randomization in DB1
- Number (%) of subjects who took at least one dose of study medication
- Number (%) of subjects who treated their migraine attack with 1 dose of study medication
- Number (%) of subjects who treated their migraine attack with 2 doses of study medication
- Number (%) of subjects who took a second dose of study medication prior to recording the 2 hours time point (LOCF)
- Duration between the first and second dose of study medication administered for one migraine attack (for subjects with 2 doses administered)

The following will be presented for the SS and FAS2:

- Number (%) of subjects who treated a second migraine attack with study medication
- The number of days between the first dosing dates of DB1 and DB2

Statistical Analysis Plan

Final V1.0

[name], Ltd.
Protocol #DFN-02-CD-012
INC Research #1007752

All study medication dosing information will be listed. For subjects who enter the DB2 period, the number of days between the first dosing dates of the DB1 and DB2 periods will also be listed.

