9.2. RESCUE MEDICATIONS

Rescue medications are defined as medications taken to treat a migraine attack (in addition to the study medication) within 24 hours after the first dose of study medication. Rescue medications taken during the study will either be reported in the eCRF based on entries in the subject eDiary, or will be reported outside of the eDiary. All rescue medications will be classified using the Anatomical Therapeutic Chemical (ATC) classification and preferred drug names from the World Health Organization Drug Dictionary (WHO-DD), version March 2016.

Summaries of rescue medications will be presented for the SS, SS1, and SS2 in tabular form using the highest level ATC term as an upper classification and the preferred drug name as a lower classification level. All medications will be summarized by dose level and sorted by descending counts in the upper classification term and the lower classification term within the upper. For each subject, the medication will be counted only once within the upper classification level and only once within the lower classification level.

The number of rescue medication doses taken will be summarized by treatment group and overall for the SS, SS1, and SS2.

Separate listings will be provided for rescue medications taken during each DB treatment period.

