 - The total number (%) of subjects who discontinued from the study and the primary reason for discontinuation
- Section 7.2: The modification of the demographics and other baseline characteristics summary:
 - Demographics and other baseline characteristics will be summarized for the SS, SS1, and SS2 by treatment group and overall, with descriptive statistics including n, mean, standard deviation, median, minimum, and maximum for numeric variables and frequency and percentage for categorical variables.
 - Section 8.1.1: The modification of the primary efficacy endpoint analysis:
 - The number of subjects with response, the number of subjects with non-missing assessment, proportions for the DFN-02 10 mg and placebo groups, 95% exact CIs for those proportions, the odds ratio for response, and the corresponding p-value will be presented for the comparison between two treatment groups for the FAS1. This analysis will exclude subjects who took a second dose of study medication or rescue medication prior to the data collection of the 2 hours postdose time point (inclusive).
 - Section 8.2: The modification of the secondary efficacy endpoint analysis:
 - The secondary efficacy endpoints that involve proportions of subjects who have a response will be summarized by treatment group and will be analyzed using the LOCF for missing secondary efficacy endpoint data.

Statistical Analysis Plan
Final V1.0

[name], Ltd.
Protocol #DFN-02-CD-012
INC Research #1007752

- Secondary efficacy endpoint analyses will be conducted as indicated for the FAS1 and FAS2 and will exclude subjects who took a second dose of study medication or rescue medication prior to the data collection of the 2 hours postdose time point (inclusive).
- Section 8.2.1: The modification of the secondary endpoint analysis for headache pain freedom at 2 hours postdose during DB2:
 - The 95% exact CIs for those proportions, the odds ratio for response, and corresponding p-value from Fisher's exact test will be computed for the comparison between treatment groups.
- Section 8.2.9: The addition of this analysis for change in functional disability score postdose:

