13.2.4. Column Headers

- Column headings should be displayed immediately below the solid line described above in initial upper-case characters.
- In the case of efficacy tables, the variable (or characteristic) column will be on the far left followed by the treatment group columns and total column (if applicable).

Statistical Analysis Plan
Final V1.0

[name], Ltd.
Protocol #DFN-02-CD-012
INC Research #1007752

P-values may be presented under the total column or in separate p-value column (if applicable). Within-treatment comparisons may have p-values presented in a row beneath the summary statistics for that treatment.

- For numeric variables, include "unit" in column or row heading when appropriate.
- Analysis set sizes will be presented for each treatment group in the column heading as (N=xx) (or in the row headings if applicable). This is distinct from the 'n' used for the descriptive statistics representing the number of subjects in the analysis set.
- The order of treatments in the tables and listings will be Placebo first in the case of placebo controlled studies and Active comparators first in the case of active comparator trials, followed by a total column (if applicable).

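### SAP 8.1.1 and 8.2 drop subjects who take a second dose or rescue by the 2-hour reading; no readable analysis scores them as non-responders, and no readable table isolates early rescue by arm

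*SAP*

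**What the plan says.** SAP 5.4 defines FAS1 and FAS2 by dosing plus some later efficacy reading, with no condition on early medication. SAP 8.1.1 then narrows the primary analysis: "This analysis will exclude subjects who took a second dose of study medication or rescue medication prior to the data collection" of the 2-hour time point, inclusive. SAP 8.2 says the secondary analyses "will exclude subjects who took a second dose of study medication or rescue medication prior to the data collection", with the same cut-off. The planned effect display is "the odds ratio for response, and the corresponding p-value will be presented for the comparison between two treatment groups for the FAS1", using Fisher's exact test.

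The rule is not hidden. Protocol 11.2 has it inside the FAS definition: patients qualify only if they "did not use a second dose of study medication or rescue medication prior to the data collection of the 2 hours postdose" reading. SAP 11 lists it under "Section 8.1.1: The modification of the primary efficacy endpoint analysis".

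The SAP table index has four primary tables: LOCF and observed data, each in FAS1 and in the PPS. Protocol 11.6.1 left further sensitivity analyses of the primary endpoint to the SAP; its readable text adds none for this event.

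On reporting, SAP 9.1 gives, by treatment group, "Number (%) of subjects who took a second dose of study medication prior to recording the 2 hours time point", followed by an LOCF tag in brackets. SAP 9.2 defines rescue as "medications taken to treat a migraine attack (in addition to the study medication) within 24 hours after the first dose of study medication", with no split at 2 hours. SAP 8.2.10 covers 2 to 24 hours only.

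**The concern.** Taking more medication before the 2-hour reading is a post-randomization event, and the likeliest reason for it is that the first dose has not worked. Removing such subjects takes probable failures out of the denominator, and the share removed can differ by arm. What remains is no longer the comparison that randomization set up. Disclosure lets a reader see the rule but does not remove the selection.

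With about 50 subjects per arm, a few exclusions can change the conclusion. As planned, the reader would not have a failure-scored result to set beside the exclusion result, nor a table showing how early rescue split between arms.

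**Working it through.** **Inputs.** SAP 3.6 and Protocol 11.8: 15% placebo, 42% DFN-02, 50 per arm, two-sided 5%. SAP 8.1.1: Fisher's exact test. Neither document gives an early-use rate, so every such rate below is an assumption.

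**The plan's own figures.** The pooled normal approximation gives 86.0% power, matching the SAP's 86%. Exact enumeration of the Fisher test gives 81.75%, close to the protocol's 81%. The exact Fisher figure is the baseline here.

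**Model.** Let p be the response rate with early users scored as failures, and e the share of an arm with early use. Assume every early user is a failure and no other data are missing.

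- Rate after exclusion = p/(1−e).
- Odds ratio after exclusion = [pD/(1−eD−pD)] / [pP/(1−eP−pP)].
- Failure-scored odds ratio = (0.42/0.58)/(0.15/0.85) = 4.10.
- Early use among failures = e/(1−p).

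Example, 20% placebo and 5% DFN-02: (0.42/0.53)/(0.15/0.65) = 0.792/0.231 = 3.43.

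Power is by exact enumeration: early users are Binomial(50, e), and responders among the rest are Binomial(50 minus early users, p/(1−e)).

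| Early use, placebo/DFN-02 | Early use among failures | Rates after exclusion | Odds ratio | Fisher power |
|---|---|---|---|---|
| none | – | 15.0% / 42.0% | 4.10 | 81.75% |
| 2% / 2% | 2.4% / 3.4% | 15.3% / 42.9% | 4.15 | 83.67% |
| 5% / 5% | 5.9% / 8.6% | 15.8% / 44.2% | 4.23 | 84.35% |
| 10% / 5% | 11.8% / 8.6% | 16.7% / 44.2% | 3.96 | 80.42% |
| 20% / 5% | 23.5% / 8.6% | 18.8% / 44.2% | 3.43 | 69.46% |
| 5% / 10% | 5.9% / 17.2% | 15.8% / 46.7% | 4.67 | 88.84% |

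**Break-even.** The odds ratio is unchanged when eD/eP = (1−pD)/(1−pP) = 0.58/0.85 = 0.68, that is, when failures in both arms use early medication equally often. Above that ratio exclusion favours DFN-02; below it, placebo.

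**Bias versus group size.** At 10%/6.8% the odds ratio stays at 4.10, yet power is 82.26% rather than 81.75%. Smaller, unequal groups alter the conservatism of Fisher's test, so power changes are not all bias.

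**No true difference (25% in each arm, failure-scored).** Rejections favouring DFN-02/placebo are 1.5%/1.5% with failure scoring. After exclusion they are 1.8%/1.8% at 5%/5%, 0.5%/5.9% at 20%/5%, and 2.7%/1.2% at 5%/10%. The 5%/5% row is symmetric, so its rise is not bias.

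**Example counts.** With 8/50 placebo and 17/50 DFN-02 responders, p = 0.063. Excluding 3 placebo and 10 DFN-02 subjects gives 8/47 and 17/40, p = 0.016. Excluding 10 and 3 gives 8/40 and 17/47, p = 0.153.

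**Scale of the planning rates.** The documents do not say whether 15% and 42% are failure-scored or after exclusion. If after exclusion, failure-scored rates are p(1−e), and the failure-scored odds ratio is 4.00 at 5%/5%, 4.25 at 10%/5% and 4.87 at 20%/5%.

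**The case against.** The rule was set in advance in both documents. It concerns use that breaches the dosing instructions (SAP 3.8), so it may be rare. Non-responder scoring is itself an assumption. If failures in both arms take early medication equally often, the odds ratio does not move. All of this stands and limits the size of the point. It does not justify having no failure-scored analysis at all.

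Three stronger readings are tempting, and the documents do not support them.

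- *That the exclusion favours DFN-02.* SAP 3.8 offers the second dose to subjects with some but inadequate relief, and partial relief might be commoner on DFN-02. But Protocol 6.1 and 9.5.2 direct patients with no relief to rescue instead, and rescue triggers the same exclusion. Failures in both arms have a route to it, so no direction follows. The DFN-02-favouring row at 5%/10% requires its failures to use early medication about 17.2/5.9 = 2.9 times as often as placebo failures.
- *That excluded subjects cannot be counted by arm.* SAP 6.1.1 puts all collected data in listings sorted by treatment group. The listings index includes second doses and rescue, and SAP 3.4 has the date and time of rescue recorded. In addition, SAP 13.2.4 says "Analysis set sizes will be presented for each treatment group in the column heading as (N=xx"), so FAS1 N minus the LOCF denominator is close to the number excluded. What is missing is a summary line.
- *That SAP 8.2.10 counts early users as non-users.* The general rule in 8.2 already excludes them there.

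One passage cuts partly the other way. The LOCF tag on the early second-dose line in SAP 9.1 suggests that such subjects may be carried forward. If their last score before the second dose were used, those still in pain would count as non-responders. That conflicts with the exclusion in 8.1.1, and the two must be reconciled.

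**Conclusion.** The point holds in limited form. SAP 8.1.1 and 8.2 select on a post-randomization event plausibly tied to first-dose failure. None of the readable primary analyses scores these subjects as non-responders, and no readable summary table isolates early rescue by arm. Section 8.2.7, section 8.3 and the table shells could not be checked. SAP 8.1.1 also leaves open whether the exclusion applies to the PPS run; if it does not, early users would enter there with observed or carried-forward scores.

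Under assumed early-use shares of 5% to 20%, the odds ratio of 4.10 moves to between 3.43 and 4.67, and Fisher power of 82% to between 69% and 89%. Part of the power change reflects group size. Heavier placebo use mainly costs DFN-02 power and does not raise false-positive efficacy. These figures assume that all early users are failures, that 15% and 42% are failure-scored rates, and that 50 per arm are analysable. With rare early use the effect would be small. The change is still worth making because it is cheap and removes the dependence on an untested selection.

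**What to change.** 1. In 8.1.1, 8.2.1, 8.2.2 to 8.2.4, 8.2.5 up to 120 minutes, and 8.2.8, keep all FAS subjects in the denominator. Score a second dose or rescue before or at the 2-hour data collection as non-response from that intake onward. Keep the present exclusion as a sensitivity analysis. Sustained pain freedom (8.2.8) needs the rule spelled out, because its definition bars other medication only from 2 to 24 hours; without the exclusion, a subject rescued earlier could count as a success.
2. For the 24-hour symptom reading in 8.2.5, either apply one rule to medication taken before and after 2 hours, or keep the current exclusion. Otherwise early users would be forced to non-response while someone rescued just after 2 hours keeps the observed status. Leave 8.2.6 and 8.2.9 to 8.2.12 under the current exclusion.
3. Add to 9.1, by arm, the number of subjects with early rescue and the number excluded for any early use.
4. Reconcile the LOCF tag in 9.1 with 8.1.1, and state whether the exclusion applies to the PPS run.

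Cost: wording in SAP 8.1.1, 8.2, 9.1 and 11, one derived flag from times already in the eDiary, the sensitivity tables and two summary lines. No new data are needed. The downside is slightly lower response rates and reliance on non-responder scoring, itself an assumption, which is why the exclusion analysis stays as a sensitivity analysis.

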8.2. SECONDARY EFFICACY ENDPOINTS AND ANALYSES

The secondary efficacy endpoints that involve proportions of subjects who have a response will be summarized by treatment group and will be analyzed using the LOCF for missing secondary efficacy endpoint data.

Secondary efficacy endpoint analyses will be conducted as indicated for the FAS1 and FAS2 and will exclude subjects who took a second dose of study medication or rescue medication prior to the data collection of the 2 hours postdose time point (inclusive).

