At postdose, patients will record time to meaningful pain relief (based on their perception), and time to pain-free after study medication within 2 hours postdose. Patients will also record their functional disability at 2 hours and 24 hours postdose, and their pain level and presence of MBS at 10, 15, 20, 30 minutes, and at 1, 1.5, 2, and 24 hours postdose. Patients will record their treatment satisfaction at 2 hours postdose, and complete the PPMQ-R questionnaire again at 24 hours postdose. Patients will also record study medication dosing and use of rescue medication in the eDiary at applicable timings.

The following eDiary assessments will be recorded by the patient in accordance with [Table 10.2](#).

- Migraine pain and symptoms:
 - Migraine pain start and end (date and time)
 - Level of headache pain predose and at various time points after (0 = none; 1 = mild; 2 = moderate; 3 = severe)
 - Time to meaningful pain relief (based on patient's perception) and time to pain-free after study medication
 - Migraine symptoms and MBS other than pain (nausea, photophobia, phonophobia, at predose, and at various time points, postdose)
 - [REDACTED]
- PPMQ-R: The PPMQ-R is a self-administered satisfaction measurement for acute migraine treatment.
- Functional disability scale (0 = no disability, able to function normally; 1 = performance of daily activities mildly impaired, can still do everything but with difficulty; 2 = performance of daily activities moderately impaired, unable to do some things; 3 = performance of daily activities severely impaired, cannot do all or most things, bed rest may be necessary).
- Overall treatment satisfaction, measured by asking questions to the patients, and the answers will be assessed on a 7-point scale (1 = very satisfied, 2 = satisfied, 3 = somewhat satisfied, 4 = neither satisfied nor dissatisfied, 5 = somewhat dissatisfied, 6 = dissatisfied, and 7 = very dissatisfied).
- Study medication and rescue use.

Visits may be scheduled as needed for AE management. Adverse event and concomitant medication review should be performed at each unscheduled visit.

CONFIDENTIAL

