6.3. MISSING DATA

Subjects are allowed to withdraw from the study at any time. Subjects who withdraw from the study will have all data listed and, wherever relevant, included in any subject summaries. Analyses on quantitative and categorical variables will include data from subjects with non-missing values. Partial dates will be listed as recorded on the case report form (CRF). Imputation of missing or incomplete dates will only be performed for summaries of AEs and concomitant medications unless otherwise specified.

Partial Missing Start or Stop Date	Imputed Start Date	Imputed Stop Date
Missing month and day, and the year is present	January 1 of that year or DB period dose date if the	December 31 of that year

Statistical Analysis Plan

Final V1.0

[name], Ltd.
Protocol #DFN-02-CD-012
INC Research #1007752

Partial Missing Start or Stop Date	Imputed Start Date	Imputed Stop Date
	year is the same as the year of the DB period dose date	
Missing day, but year and month are present	First day of that month or DB period dose date if the year and month are the same as the year and month of the DB period dose date	Last day of that month
Missing month, but year and day are present	Missing month imputed as January	Missing month imputed as December

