8.2.5. Freedom from Nausea, Photophobia, and Phonophobia Postdose

The proportion of subjects who are free from nausea, photophobia, and phonophobia at 10, 15, 20, 30, 60, 90, 120 minutes and 24 hours after the first dose of study medication taken for a migraine attack during each DB treatment period will be summarized by symptom, treatment group, and time point for the FAS1 and FAS2. The corresponding p-values from Fisher's exact test will be computed for the comparison between treatment groups. Subjects who report a symptom pre-dose and report the status of the symptom at the particular postdose time point will be analyzed.

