8.2.8. Sustained Headache Pain Freedom at 24 Hours

The proportion of subjects who have sustained headache pain freedom at 24 hours (from 2 to 24 hours) after the first dose of study medication taken for a migraine attack during each DB treatment period will be summarized by treatment group for the FAS1 and FAS2. Sustained headache pain freedom at 24 hours is defined as pain free at 2 hours postdose, with no use of rescue medication or additional study medication and no recurrence of headache pain within 2 to 24 hours postdose. The corresponding p-values from Fisher's exact test will be computed for the comparison between treatment groups.

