Final V1.0

[name], Ltd.
 Protocol #DFN-02-CD-012
 INC Research #1007752

Number	Title	Population
	Using LOCF	
14.2.2.7.1	Secondary Efficacy Analysis on Absence of Most Bothering Symptom (MBS) among Nausea, Photophobia, and Phonophobia at 10, 15, 20, 30, 60, 90, and 120 Minutes Postdose During DB2 Using LOCF	FAS2
14.2.2.8.1	Secondary Efficacy Analysis on Freedom from Nausea, Photophobia, and Phonophobia at 10, 15, 20, 30, 60, 90, and 120 Minutes Postdose Time Point During DB1 Using LOCF	FAS1
14.2.2.9.1	Secondary Efficacy Analysis on Freedom from Nausea, Photophobia, and Phonophobia at 10, 15, 20, 30, 60, 90, and 120 Minutes Postdose During DB2 Using LOCF	FAS2
14.2.2.10.1	Secondary Efficacy Analysis on Time to Meaningful Headache Pain Relief During DB1	FAS1
14.2.2.10.2	Secondary Efficacy Analysis on Time to Meaningful Headache Pain Relief During DB2	FAS2
14.2.2.11.1	Secondary Efficacy Analysis on Time to Headache Pain Freedom During DB1	FAS1
14.2.2.11.2	Secondary Efficacy Analysis on Time to Headache Pain Freedom During DB2	FAS2
14.2.2.12.1		FAS1
14.2.2.13.1		FAS2
14.2.2.14.1	Secondary Efficacy Analysis on Sustained Headache Pain Freedom from 2 to 24 Hours Postdose During DB1	FAS1

Statistical Analysis Plan

Final V1.0

[name], Ltd.
 Protocol #DFN-02-CD-012
 INC Research #1007752

Number	Title	Population
14.2.2.14.2	Secondary Efficacy Analysis on Sustained Headache Pain Freedom from 2 to 24 Hours Postdose During DB2	FAS2
14.2.2.15.1	Secondary Efficacy Analysis on Postdose Change in Functional Disability Score During DB1	FAS1
14.2.2.15.2	Secondary Efficacy Analysis on Postdose Change in Functional Disability Score During DB1 by Score Category	FAS1
14.2.2.16.1	Secondary Efficacy Analysis on Postdose Change in Functional Disability Score During DB2	FAS2
14.2.2.16.2	Secondary Efficacy Analysis on Postdose Change in Functional Disability Score During DB2 by Score Category	FAS2
14.2.2.17.1	Secondary Efficacy Analysis on Use of Second Study Medication Dose or Rescue Medication During DB1	FAS1
14.2.2.17.2	Secondary Efficacy Analysis on Use of Second Study Medication Dose or Rescue Medication During DB2	FAS2
14.2.2.18.1	Secondary Efficacy Analysis on Subject-Rated Treatment Satisfaction at 2 Hours Postdose During DB1	FAS1
14.2.2.18.2	Secondary Efficacy Analysis on Subject-Rated Treatment Satisfaction at 2 Hours Postdose During DB2	FAS2

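### SAP 8.2 applies LOCF to secondary response proportions without exempting 24-hour outcomes, and the table index points the other way for sustained pain freedom

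*SAP*

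**What the plan says.** SAP 8.2 sets the general rule. It covers "The secondary efficacy endpoints that involve proportions of subjects who have a response", and these "will be analyzed using the LOCF for missing secondary efficacy endpoint data". SAP section 11 repeats the sentence as a change from the protocol. Neither place exempts an endpoint or a time point.

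SAP 8.2.8 makes sustained pain freedom a proportion compared by Fisher's exact test, "defined as pain free at 2 hours postdose, with no use of rescue medication or additional study medication and no recurrence of headache pain" between 2 and 24 hours. It does not say what happens when the 24-hour rating is absent.

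Protocol 10.2.1.4.1 has patients record "their pain level and presence of MBS at 10, 15, 20, 30 minutes, and at 1, 1.5, 2, and 24 hours postdose". The 24-hour rating is therefore the only scheduled pain rating after 2 hours.

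Two places point away from LOCF. The index of tables lists "Secondary Efficacy Analysis on Sustained Headache Pain Freedom from 2 to 24 Hours Postdose During DB1" (14.2.2.14.1) with no LOCF label, and likewise 14.2.2.14.2 for DB2. The tables for early pain freedom, pain relief, most bothersome symptom and symptom freedom all carry the label. SAP 6.3 also says "Analyses on quantitative and categorical variables will include data from subjects with non-missing values".

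SAP 8.2.5 extends symptom freedom to "120 minutes and 24 hours after the first dose of study medication", but the titles of its LOCF tables (14.2.2.8.1 and 14.2.2.9.1) stop at 120 minutes.

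**The concern.** The endpoint has to show "no recurrence of headache pain within 2 to 24 hours postdose". For a patient who is Grade 0 at 2 hours and has no 24-hour rating, the last observation is that Grade 0. Carrying it forward supplies the non-recurrence instead of observing it. Only 2-hour responders can gain from this. If ratings go missing equally often in both arms, the arm with more 2-hour responders gains more, and the treatment difference moves in its favour.

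The conflict with the index matters as well. Two programmers could build table 14.2.2.14.1 in two ways and each cite the SAP. Which way is used should not be left open until treatment codes are known.

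**Working it through.** **Which rule applies.** The documents give no sustained-freedom rate to reproduce, so the texts come first.

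- Towards LOCF: SAP 8.2 is broad enough to include sustained freedom. Protocol 11.6.2 analyses sustained freedom in the same manner as the primary endpoint, and protocol 11.6.1 runs that endpoint with both LOCF and observed data.
- Away from LOCF: for 2-hour pain freedom the index pairs a labelled table with an unlabelled one (14.2.1.1.1 with .2, and 14.2.2.1.1 with .2). This matches the separate LOCF and observed displays in SAP 8.1.1, so an unlabelled title suggests observed data.
- SAP 6.3 does not settle it, because 8.1.1 and 8.2 impose LOCF despite that general sentence.

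**Size if 8.2 is followed as written.** Inputs:

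- p, pain-free at 2 hours: 42% DFN-02 and 15% placebo (SAP 3.6).
- r, share of 2-hour responders with recurrence or rescue: 40% in both arms (assumption).
- m, share without a 24-hour rating: 10%, 20% or 30% in both arms, unrelated to outcome (assumption).

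Formulas:

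- True sustained rate: p(1 − r)
- LOCF: p[(1 − m)(1 − r) + m]
- Missing counted as not sustained: p(1 − m)(1 − r)

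True rates are 0.42 × 0.6 = 25.2% and 0.15 × 0.6 = 9.0%, a difference of 16.2 points.

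| m | LOCF, DFN-02 v placebo | Difference | Missing as not sustained | Difference |
|---|---|---|---|---|
| 10% | 26.9% v 9.6% | 17.3 | 22.7% v 8.1% | 14.6 |
| 20% | 28.6% v 10.2% | 18.4 | 20.2% v 7.2% | 13.0 |
| 30% | 30.2% v 10.8% | 19.4 | 17.6% v 6.3% | 11.3 |

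The LOCF excess in the difference is (0.42 − 0.15) × r × m = 0.27 × 0.4 × m, or 1.1, 2.2 and 3.2 points. At 50 per arm that is a net 0.5 to 1.6 subjects.

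**Recorded rescue.** The LOCF formula credits every responder without a rating. Those with a recorded rescue or second dose still fail. If half of the 40% were recorded rescue (assumption), the excess is 0.27 × 0.2 × m, or about 0.5, 1.1 and 1.6 points.

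**Range for r.** With r from 10% to 50%, the excess at m = 10% is 0.27 to 1.35 points, and at m = 30% it is 0.81 to 4.05 points. The true difference, 0.27 × (1 − r), runs from 24.3 down to 13.5 points.

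**If missingness is not neutral.** If every responder without a rating had in fact recurred unrecorded (possible while m is below r), the excess would be 0.27 × m, or 2.7, 5.4 and 8.1 points. If placebo missingness exceeded 0.42 / 0.15 = 2.8 times that on DFN-02, with equal r, LOCF would favour placebo instead.

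**Which rule is nearer the truth.** Counting missing as not sustained understates the difference by 0.27 × (1 − r) × m, which at r = 40% is 1.6, 3.2 and 4.9 points. That is more than the LOCF error at each m. With neutral missingness, LOCF is the closer of the two whenever r is below 50%.

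**Observed cases.** Dropping only the responders who lack a rating keeps every 2-hour non-responder in the denominator. At m = 10% this gives 22.68 / 95.8 = 23.7% v 8.1 / 98.5 = 8.2%, about 15.5 points. Dropping all subjects without a rating returns 25.2% v 9.0% under the neutral assumption.

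**The case against.** A reader might infer that the SAP lays down LOCF for every proportion endpoint, and that a responder without a 24-hour entry is definitely counted as sustained. The documents do not go that far. The 8.2 sentence is limited to response proportions, no passage states that outcome for sustained freedom, and the index leaves the LOCF label off these tables and off the second dose/rescue tables (14.2.2.17.1 and .2). This stands, and it limits the point to what follows if 8.2 is applied as written. It does not remove the point, because a table title does not override the analysis text.

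A reader might also infer that 24-hour symptom freedom is carried forward. SAP 8.2.5 restricts the analysis to subjects who report the symptom's status at the time point in question, which reads as observed-case, and the LOCF table titles stop at 120 minutes. However, 8.2.3 and 8.2.4 contain the same kind of restriction and their tables are labelled LOCF, so the sentence does not decide it. For 24-hour symptoms the rule is unclear; inflation is not shown.

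Rescue can be known without a 24-hour rating: SAP 9.2 allows it to be reported outside the eDiary, and medication is reviewed at Visits 3 and 4. This stands, so the main figures are upper values for neutral missingness.

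Finally, counting missing as not sustained is further from the truth than LOCF at r = 40%. This stands too. The case for changing the rule is that LOCF assumes the very thing to be shown, in the favourable direction. Numerical accuracy is not the argument.

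**Conclusion.** The plan needs correcting here. The general LOCF sentence reaches a 24-hour outcome for which the carried value presupposes the answer, 8.2.8 has no rule of its own, and the index conflicts with the text. The effect is modest: at most about 1.1 to 3.2 points on a true 16.2. This rests on the plan's 42% v 15%, an assumed 40% recurrence or rescue in both arms, and 10% to 30% missing in both arms unrelated to outcome. It is smaller where rescue is recorded and larger if patients who recur are the ones who stop reporting.

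It would be too strong to say that the plan will inflate sustained response. That depends on which of the two conflicting texts is followed and on how many ratings are missing, which the documents do not say. The primary 2-hour endpoint is unaffected by this point.

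**What to change.** Before unblinding:

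- **SAP 8.2:** limit the LOCF sentence to time points up to and including 2 hours.
- **SAP 8.2.8:** state that a recorded rescue, second dose or recurrence is a failure. State that a 2-hour responder without a 24-hour rating is not carried forward and is counted as not sustained, as the conservative analysis. Present beside it an observed-case analysis that excludes all subjects without a 24-hour rating, whatever their 2-hour status.
- **SAP 8.2.5:** state that LOCF does not apply at 24 hours.
- **SAP 15:** make the titles for sustained freedom and symptom freedom name the missing-data rule, and cover the 24-hour symptom time point.

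The cost is a few sentences, some retitled tables and an added observed-case display; no data collection changes. The downside is that the conservative rule lowers the sustained rates in both arms and shrinks the treatment difference, to 14.6, 13.0 and 11.3 points at 10%, 20% and 30% missing under the assumptions above. It should be described as conservative, not unbiased.
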